#### **6.1.4.2. SAS Code for Multiple Imputation**

See below for SAS code describing the multiple imputation approach.

Step 1:

```
proc mi data=&base._tr out=&base._mcmc seed=432832 nimpute=10
minimum=0 maximum=&maxval. round=1;
  mcmc impute=monotone prior=jeffreys;
  em maxiter = 300;
  var visit1-visitN;
run;
```

Step 2:

```
proc mi data=&base._mcmc seed=931428 nimpute=15 out=&base._pmm
minimum=0 maximum=&maxval. round=1;
  by _imputation1_;
  class sexn trt01pn countryn;
  monotone regpmm(visit1-visitN) ;
  var sexn age trt01pn countryn visit1-visitN;
run;
```

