### **6.1.4. Handling of Dropouts or Missing Data**

For the primary efficacy analysis, subjects with a missing SSS at either 6- or 9- hours will be given an “average” SSS at 6 and 9 hours equal to the single score that is available from this time period. For subjects with missing SSS’s at both 6 and 9 hours, the site investigator will be asked to use all available contemporaneous clinical and laboratory data to determine the SSS at these time points. These scores will be obtained and finalized prior to database lock to ensure that investigators are blinded during this process. Finally, if missing data persists after the prior methods, then multiple imputation will be performed based on country, gender, baseline age, baseline SSS scores, treatment assignment, and available post-baseline SSS scores. Subscores

will be imputed and then the SSS score will be derived. More details on the multiple imputation process are provided in [Section 6.1.4.1](#) below.

For the first key secondary endpoint, AUC of the SSS through Day 7, for any missing data, the site investigators will again be asked to use all available contemporaneous clinical and laboratory data to determine the SSS at these time points. If data are still missing, multiple imputation will be used to determine missing scores and subscores based on country, baseline age, gender, baseline SSS scores, treatment assignment, and available post-baseline SSS scores. More details on the multiple imputation process are provided in [Section 6.1.4.1](#) below.

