#### 6.1.4.1. Multiple Imputation

The multiple imputation (MI) procedures for the primary and key secondary endpoints are described below.

For the primary analysis, missing data not due to mortality, and not addressed by the averaging rules above, will be imputed using the following regression-based multiple imputation model.

The following imputation algorithm will be applied to each SSS subscore separately, then the primary outcome SSS score will be derived.

1. The first step is to understand the pattern of missingness. In order to perform the multiple imputation, a monotone missing pattern must be achieved. For example, if there exist values for baseline and Day 2 visits, but missing values for the Day 1 (8-10h) visit, Markov-Chain Monte-Carlo (MCMC) method will be used to impute the small amount of missing data that may be missing at the intermediate visits that is required to make the missing data pattern monotone before applying the multiple imputation algorithm. This method uses a non-informative Jeffreys prior to derive the posterior mode from the expectation-maximization (EM) algorithm as the starting values for the MCMC method. This MCMC method will use seed of 432832. To avoid values that could not be observed in practice, imputed values will be constrained to be integers in the range of 0 to 3 or 0 to 4 by convention to align with the scale of the questionnaire. A total of 10 imputations will be done in the MCMC step.
2. Once the monotone pattern is achieved, the next step is to implement the imputation algorithm. For this, the Predictive Mean Matching method (PMM) will be used. This method is particularly helpful if the normality assumption is violated. For subjects with complete data up to a particular visit, a PMM model will be fit that includes the outcome at that visit as the dependent variable; and as independent variables gender, treatment assignment, study site, and non-missing scores using a seed of 931428. This process will be repeated 15 times, resulting in a total of 150 complete analysis datasets.
3. For each completed dataset, any necessary derived variables will be computed. Then the ANCOVA model will be performed for the 6 and 9 hour average SSS score. The results will be combined into one MI inference (LS mean, associated 95% CI, and p-value) using PROC MIANALZE as illustrated (Ratitch et al., 2013).

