#### **6.1.6. Pooling of Sites**

The question of pooling of sites does not arise since study sites will not be taken into account in the analyses.

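### The first imputation step in SAP 6.1.4.2 omits treatment, country, sex and age, so 6- and 9-hour scores filled there are drawn partly toward no difference; the 6.1.4.1 prose also gives a different predictor list for the second step

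*SAP*

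**What the plan says.** SAP 6.1.4 sets an order for missing primary-endpoint data. If one of the 6- and 9-hour scores is missing, the other stands for the average. If both are missing, the blinded site investigator is asked to reconstruct the score from contemporaneous records. Only what is still missing goes to imputation: "multiple imputation will be performed based on country, gender, baseline age, baseline SSS scores, treatment assignment", together with available post-baseline scores. Deaths are handled apart, with a score of 16 (6.1.7.1).

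Section 6.1.4.1 describes two steps, run on each subscore. Step 1 uses MCMC to fill intermittent gaps, so that the missing pattern becomes monotone; the prose gives it no predictor list. Step 2 uses predictive mean matching for what remains, with "as independent variables gender, treatment assignment, study site, and non-missing scores".

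Section 6.1.4.2 gives the code. Step 1 opens with "proc mi data=&base._tr out=&base._mcmc seed=432832 nimpute=10" and specifies "mcmc impute=monotone prior=jeffreys". Its VAR statement holds only `visit1-visitN`, and there is no BY statement for arm. Step 2 has "var sexn age trt01pn countryn visit1-visitN".

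Section 6.1.6, on pooling, says that "study sites will not be taken into account in the analyses". Section 6.1.4.1 applies the same two-step process to SSS-AUC, NPRS-AUC and Day 2 CGI-I.

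**The concern.** An imputation model should contain the variable that the analysis will test. If treatment is left out, a missing score is drawn from a relationship averaged over both arms. The imputed values then show an arm difference only so far as the patient's other scores carry it.

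Here the omission sits in the step that matters for a particular kind of patient. Someone with neither a 6- nor a 9-hour score but with a Day 2 score has an intermittent gap. Step 1 fills it, and step 2, which does contain treatment, has nothing left to impute at those times.

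At stake are some attenuation of the primary estimate and its confidence interval, and some power. Because the primary test opens the fixed sequence (8.1.2), lost power there passes to all four key secondary endpoints. Three of those are themselves imputed in this way. For NPRS and CGI-I, 6.1.4 describes no investigator reconstruction beforehand.

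The second issue is one of specification. SAP 4.1 calls the study confirmatory, so the imputation model for the primary endpoint should be stated once and the same way everywhere.

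**Working it through.** **1. The predictor lists side by side**

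| Place | Treatment | Country | Site | Sex | Age | Scores |
|---|---|---|---|---|---|---|
| 6.1.4 text | yes | yes | no | yes | yes | yes |
| 6.1.4.1 prose, step 2 | yes | no | yes | yes | no | yes |
| 6.1.4.2 code, step 1 | no | no | no | no | no | yes |
| 6.1.4.2 code, step 2 | yes | yes | no | yes | yes | yes |

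The 6.1.4 text and the step 2 code agree. The step 1 code and the 6.1.4.1 prose each depart from them. The SAP does not define `visit1`; I take it to be baseline, because 6.1.4.1 counts baseline as part of the visit pattern.

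**2. Which step fills the 6- and 9-hour scores**

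- One of the two observed: the averaging rule settles the endpoint, without imputation.
- Death before or between the two times: 16 is assigned.
- Both missing, reconstruction succeeds: no imputation.
- Both still missing, a later score exists: step 1, without treatment.
- Both still missing, no later score: step 2, with treatment.

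**3. The plan's own sample size**

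Inputs from SAP 3.2: difference 1.1, SD 1.75, two-sided alpha 0.05, power 85%, 1:1, 94 patients.

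Normal approximation: n per arm = 2(1.960 + 1.036)² × 1.75² / 1.1² = 45.5, so 46 per arm and 92 in total. With the noncentral t distribution, power is 84.7% at 46 per arm and 85.4% at 47 per arm. The stated 94 reproduces, and 85.4% is the reference power below.

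**4. Size of the attenuation**

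Let m be the share of patients whose 6- and 9-hour scores are filled in step 1, and d_imp the expected arm difference among those imputed scores. Then

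expected difference = (1 − m) × 1.1 + m × d_imp.

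For d_imp, let S be the within-arm covariance of the scores at baseline, 3, 6 and 9 hours and Days 2, 3 and 7, and d the vector of arm differences at those visits. With 1:1 allocation, a model without treatment sees P = S + dd′/4. Regressing the missing pair on the observed visits gives B = P_mo P_oo⁻¹, and d_imp is the mean of B d_o over 6 and 9 hours.

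Assumptions, since the documents give none of these: m of 2%, 5% or 10%; first-order autoregressive correlation ρ between successive visits; S scaled so that the change to the 6/9-hour average has SD 1.75. Three effect profiles, each with 1.1 at 6 and 9 hours:

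- *Worst case*: no arm difference at any other visit, so d_imp = 0 whatever ρ is.
- *Intermediate*: 0.5 at 3 hours, 0.8 at Day 2, 0.5 at Day 3, 0.2 at Day 7; d_imp = 0.62 at ρ = 0.7.
- *Favourable*: 1.1 at every post-baseline visit; d_imp = 1.0 at ρ = 0.7.

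For example, at m = 5% the intermediate case is 0.95 × 1.1 + 0.05 × 0.62 = 1.045 + 0.031 = 1.076.

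| m | Worst: difference, power | Intermediate: difference, power | Favourable: difference, power |
|---|---|---|---|
| 2% | 1.078, 84.0% | 1.090, 84.8% | 1.098, 85.3% |
| 5% | 1.045, 81.7% | 1.076, 83.9% | 1.095, 85.1% |
| 10% | 0.990, 77.4% | 1.052, 82.2% | 1.090, 84.8% |

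Power is by noncentral t at 47 per arm and ignores the information lost to missing data. Letting ρ run from 0.5 to 0.9 moves the intermediate d_imp from 0.49 to 0.68, and the 10% figure from 1.039 to 1.058. With treatment in step 1 the expected difference stays at 1.1.

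**The case against.** The strongest reply is that very few patients are affected. Imputation is the last resort, and the patient who misses both scores but is seen on Day 2 is the one that reconstruction is meant to rescue. SAP 6.1.4.1 itself expects little intermittent missing data. The 15% withdrawal in 3.2 runs to the end of the study, not to 9 hours, so even 10% is generous. The example in 6.1.4.1 lacks only the 8–10 hour score; if the 5–6 hour score is there, the averaging rule settles the primary endpoint. All of this stands. A reader might infer that step 1 supplies the primary result for many patients, but the documents give no rate that would support it.

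Three other strong readings also fail. It is tempting to say that step 1 drops every promised predictor, but baseline and post-baseline scores are in it, and that is why the pull is only partial. It is tempting to say that all the lists disagree, but 6.1.4 and the step 2 code match. And the two versions of step 2 could give different results, but nothing shows by how much. Section 6.1.6 concerns pooling in the analyses, so it is only weak evidence about an imputation model.

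The bias is indeed conservative. If there is no treatment effect, a model that ignores treatment creates none.

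The tipping point analysis in 6.1.4.3 is not an answer, however. It moves missing values only toward the null, so it can neither reveal nor undo attenuation that is already toward the null.

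**Conclusion.** The concern holds in a limited form. As written, the step 1 code departs from 6.1.4, and it imputes without treatment the 6- and 9-hour scores of any patient left with both missing and a later score observed. The step 2 prose departs from both 6.1.4 and its own code.

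Relative to 1.1, the intermediate profile loses about 2% at 5% imputed (0.024/1.1) and about 4% at 10% (0.048/1.1). The loss cannot exceed m itself unless the arm difference reverses at other visits. These sizes rest on assumed missing shares, correlations and effect profiles, and on the total score, whereas the SAP imputes bounded integer subscores. The direction and the mismatch between text and code do not depend on those assumptions. The numerical impact is probably small. The reason to act is that the error is plain and cheap to remove in the primary analysis of a study the SAP calls confirmatory. The effect on the key secondary endpoints was not calculated.

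**What to change.** Before unblinding:

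1. In 6.1.4.2 step 1, add treatment, age, sex and country to the VAR list, coded as numeric indicators where categorical and placed before the visit scores. Do this for every endpoint that uses the process.
2. In 6.1.4.1, replace study site with country and baseline age, and state the step 1 predictors, so that 6.1.4, 6.1.4.1 and both code steps share one list.

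Running step 1 separately by arm would also bring treatment in, but it halves the data, to about 47 to 55 patients per arm, for estimating a multi-visit covariance in each sparse subscore. Adding treatment to the list is the safer choice.

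The cost is a few lines of code and a sentence or two of SAP text. The predictors are already in step 2, so no new data are needed. The revised step 1 should be test-run on blinded data with dummy treatment codes, to confirm that it converges for the sparser subscores.

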#### **6.1.4.3. Tipping Point Analysis**

A sensitivity analysis for the primary endpoint will be performed by creating a table in which each patient who is missing primary outcome data is represented. For each of these patients, all possible values for the primary outcome that go towards the null hypothesis (i.e., decreasing SSS score for Placebo subjects and increasing SSS scores for Varespladib-Methyl subjects) will be examined and the p-value for the primary efficacy endpoint will be recalculated. This analysis will show the range of outcomes for which the results of the primary analysis shift from significant (i.e.,  $\alpha \leq 0.05$ ) to non-significant (i.e.,  $\alpha > 0.05$ ).

#### **6.1.5. Analysis Visit Windows**

Statistical analyses will be based on the assessment schedule described in the protocol.

#### **6.1.6. Pooling of Sites**

The question of pooling of sites does not arise since study sites will not be taken into account in the analyses.

## 6.1.7. Derived Variables

### 6.1.7.1. Primary Endpoint: Change in SSS from Baseline to Average at 6 and 9 hours

The primary endpoint SSS will be calculated from responses to the pulmonary, cardiovascular, hematologic, renal, and nervous system sections of the SSS. The sum of the values of the 5 subsections will be the total SSS used to calculate the primary endpoint. The primary endpoint will be the change from baseline to the average of the 6 hr and 9 hr scores: Change = (Baseline - [6hr + 9hr]/2). As such, a negative score will indicate an increase in severity from baseline (subject has gotten worse), and a positive score will indicate a decrease in severity from baseline (subject has gotten better). A subject who dies *before* 6 hours will receive the worst possible score (score = 16) to represent the SSS at 6 and 9 hrs. A subject who dies *between* the 6 and 9-hour period will receive the worst possible score (score = 16) at 9 hours, and this value will be averaged with the score at 6 hours for calculating the primary endpoint.

### 6.1.7.2. SSS-AUC7d

The AUC calculation includes the pulmonary, cardiovascular, local wound, hematologic, renal, and nervous system sections of the SSS assessment up to 7±1 days. The calculation will include the baseline assessment. All assessments within baseline and baseline + 8 days will be included in the calculation. This endpoint will be analyzed according to the missing data procedures described in [Section 6.1.4](#) above.

In order to standardize the duration of time for each SSS-AUC7d calculation, the “Day 7” SSS will be set at exactly 168 hours regardless of when it was actually assessed for this endpoint, with two exceptions:

- 1) For patients whose “Day 7” score was assessed prior to Day 7 (prior to 144 hours) and whose score is higher at the “Day 14” assessment than at the “Day 7” assessment, we will linearly interpolate between the “Day 7” and “Day 14” scores to impute the score at 168 hours.
- 2) For patients whose “Day 7” occurs on Day 10 or later (240 hours), we will linearly interpolate between “Day 3” and “Day 7” to impute the score at 168 hours.

The AUC will be calculated using the trapezoidal rule: average the SSS scores between two adjacent timepoints, multiply by the difference in time points in hours, repeating this across all time points and summing the results to obtain the total AUC across a fixed range of time. Thus the AUC at a particular timepoint  $j$  is calculated as follows.

$$AUC_j = \frac{1}{2}(SSS_j + SSS_{j-1})(t_j - t_{j-1})$$

where  $t$  is measured in hours;  $j = 1, \dots, J$ ; and  $J$  is the total number of timepoints at which SSS is measured.  $J = 6$  if all planned SSS assessments are performed. Thus the total AUC for subject  $i$  from baseline to Day 7 is as follows.

$$AUC_{i, \text{BL to Day 7}} = \frac{1}{2} \sum_{j=1}^J (SSS_{i,j} + SSS_{i,j-1})(t_{i,j} - t_{i,j-1})$$

Thus AUC is calculated for each subject with baseline and post-baseline SSS scores, subject to the constraints on missingness described above. An example of this applied in SAS is provided at [lexjansen.com/wuss/2004/posters/c\\_post\\_the\\_sas\\_calcuations\\_pdf](http://lexjansen.com/wuss/2004/posters/c_post_the_sas_calcuations_pdf)

- where: The SSS assessments  $SSS_0, SSS_1, \dots, SSS_J$  are made at times  $t_0, \dots, t_J$
- $t_0$  is the time of the initiation of the IV infusion
- $SSS_0$  is the SSS assessment at baseline
- $t_j$  is the  $j^{\text{th}}$  timepoint at which SSS is assessed such that  $t_j - t_0 \leq 7$  day

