5.3 Summary of Potential Risks and Benefits

The potential benefits of study participation are that subjects suffering from snakebite envenoming may receive improved outcome in terms of snakebite severity and quality of life (QoL) assessments. Table 2 describes the limitations of current serum-based antivenoms, and the potential advantages of varespladib or varespladib-methyl.

Table 2 Comparison of Varespladib and Currently Available Serum-Based Antivenom Therapies

Challenge or	Limitations of Serum-Based	Potential Advantages of Oral	
Limitation	Antivenom Therapy	Varespladib	
	Must be administered IV in a clinical setting: cannot be self-administered at the time of snakebite	In the clinic, oral and IV formulations can be administered in combination with antivenom therapies.	
Ease of Use	Intensive monitoring for antivenom induced complications required	If proven effective, an oral varespladib formulation could eventually be administered at the time of the snakebite—before reaching a hospital	
Species Specificity	Generally specific to one species or closely related species of venomous snakes and sPLA ₂ is poorly antigenic	Varespladib is a potent, broad-spectrum inhibitor of snake venom sPLA ₂	
Tissue Penetration	Large proteinaceous molecules with limited or no ability to penetrate tissues	Small molecules with the ability to penetrate tissues to neutralize or reverse sPLA ₂ -mediated venom toxicities	
Potential for Allergenicity	High	Low (no documented allergies)	
Cost to	Higher	Lower	
Manufacture	77 (2 1 1)	27 21	
Requirement for Refrigeration	Yes (most formulations)	No refrigeration	
Available Global Supply	Current and anticipated long-term global shortage (Williams, et al., 2019)	Potential for a comparably broader, more cost-effective, global distribution	

Abbreviations: IV = intravenous; $sPLA_2$ = secreted phospholipase A2.

The proposed dosing of varespladib-methyl for adult subjects consists of an initial loading dose of 500 mg ($2 \times 250 \text{ mg}$ oral tablet), an additional 250 mg dose ($1 \times 250 \text{ mg}$ oral tablet) approximately 12 hours later, and then 250 mg ($1 \times 250 \text{ mg}$ tablet) twice daily (BID) for the remainder of the study period. Pediatric subjects (ages 5 to < 18) will be administered doses of varespladib-methyl determined by allometric scaling, provided as 50 mg capsules (Section 7.3).

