9 TREATMENTS

9.1 Identification of Investigational Products or Placebo

The IP used in this study is varespladib-methyl along with matching placebo. Varespladib-methyl will be provided as an oral formulation.

Varespladib-methyl

- Varespladib-methyl (LY333013) is an immediate-release, oval, white, film-coated tablet at a dosage strength of 250 mg for oral administration.
- Scaled pediatric doses of varespladib-methyl (LY333013) are supplied as 50 mg immediate-release capsules for oral administration.

Placebo

- The oral placebo is supplied as a white film-coated oval tablet to match the appearance of the LY333013 250 mg tablet and contains a subset of the excipients present in the active tablet formulation: lactose monohydrate, microcrystalline cellulose, and magnesium stearate.
- Placebo for scaled pediatric dosing is supplied as an immediate-release capsule to match the LY333013 50 mg capsule, and contains the excipients lactose monohydrate, microcrystalline cellulose, and magnesium stearate.

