#### **6.1.7.15. Data Adjustments/Handling/Conventions**

All collected data will be presented in listings. Data not subject to analysis according to this plan will not appear in any tables or graphs but will be included only in the data listings.

Day 1 will refer to activities that occurred at baseline through the first 12 hours after the patient receives the study drug (regardless of whether the calendar day has changed). Day 2 assessments will occur at least 12 hours and not more than 18 hours after the 8-10 hour assessment on Day 1. Thereafter, Day will refer to calendar day following the initiation of treatment (e.g., Day 28 will occur 27 days after the day on which the patient received their first dose of study drug).

*P* values will be displayed with two significant figures if the value is greater than or equal to 0.01 (eg., 0.XX) and with one significant figure is less than 0.01 (eg., 0.00X). If a *P* value less than 0.0001 occurs, it will be shown in tables as < 0.0001.

Adverse events will be coded using the latest MedDRA version thesaurus.

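### SAP 6.1.7.2: the SSS-AUC rules fail as written for time zero and for late Day 7 visits (an IV origin for an oral drug, limits that exclude visits an exception needs, and a Day 10 hour that does not match Day 7)

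*SAP*

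**What the plan says.** All of the following is in SAP 6.1.7.2 unless noted.

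- **Time zero.** The origin of the AUC "is the time of the initiation of the IV infusion". Protocol 9.1 states: "Varespladib-methyl will be provided as an oral formulation". SAP 3.4 likewise describes only oral tablets and capsules.
- **Inclusion, first statement.** "All assessments within baseline and baseline + 8 days will be included in the calculation".
- **Inclusion, second statement.** The list under the formula defines each assessment time as a "timepoint at which SSS is assessed such that" its distance from time zero does not exceed 7 days.
- **End point.** To give every patient the same duration, the Day 7 "SSS will be set at exactly 168 hours regardless of when it was actually assessed for this endpoint", with two exceptions. The first concerns visits before Day 7, glossed as before 144 hours, when the Day 14 score is higher than the Day 7 score. The second interpolates between Day 3 and Day 7 when the Day 7 visit "occurs on Day 10 or later (240 hours".
- **Day numbering (SAP 6.1.7.15).** After Day 2, days are counted so that "Day 28 will occur 27 days after the day on which the patient received their first dose of study drug".
- **Visit window (protocol Schedule of Events and Figure 1 notes).** Day 7 is 7 days ± 1 day after the initial dose.

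**The concern.** This AUC is tested second in the fixed sequence of SAP 8.1.2. If it fails, total antivenom use, the NPRS AUC and CGI-I at Day 2 are not formally tested. The SAP calls itself a priori (section 1) and confirmatory (section 4.1), so a programmer should be able to produce one value per patient from the text alone.

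Read literally, the text does not allow that. The drug has no infusion. The treatment the protocol describes as intravenous is antivenom (protocol 5.3, Table 2: "Must be administered IV in a clinical setting"). Its first dose may or may not be complete at enrolment, so an origin tied to it would vary between patients and could fall before or after the first dose. The late-visit exception calls for scores that the inclusion limits remove. A removed score would count as missing and pass to investigator re-scoring or multiple imputation under SAP 6.1.4.

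**Working it through.** **Inputs.** Planned post-baseline SSS visits through Day 7 are at 3-4 h, 5-6 h, 8-10 h, Day 2, Day 3 and Day 7. That is six, matching J = 6 in the SAP. The documents give no SSS trajectories, so the profiles below are assumed, with early visits at 0, 3.5, 5.5, 9, 24 and 48 h.

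**1. Limits in hours.** Baseline + 8 days = 8 × 24 = 192 h. Seven days = 7 × 24 = 168 h. The second exception starts at 240 h. Since 240 > 192 > 168, neither limit admits any visit that this exception covers.

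**2. Day-to-hour rule, in 24-hour blocks from the dose.**

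| Rule | Day 7 | Day 10 |
|---|---|---|
| (d − 1) × 24, as in SAP 6.1.7.15 | 144 h | 216 h |
| d × 24 | 168 h | 240 h |
| SAP 6.1.7.2 | 144 h | 240 h |

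Neither rule reproduces the SAP pair. A visit at 216 to 240 h is on Day 10 by the SAP's own day numbering, so it is interpolated. By the stated hour it has not reached the cut-off, so it is placed at 168 h.

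**3. Size for such a visit.** The trapezoidal rule is AUC = ½ Σ (S_j + S_{j−1})(t_j − t_{j−1}).

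Profile A has scores 6, 6, 5, 4, 3, 2, then 1 at Day 7.
- Baseline to 48 h: 21 + 11 + 15.75 + 52.5 + 60 = 160.25.
- Day 7 score placed at 168 h: 160.25 + ½(2 + 1)(120) = 340.25.
- Visit at 230 h, interpolated: score at 168 h = 2 − (168 − 48)/(230 − 48) = 2 − 120/182 = 1.341. AUC = 160.25 + ½(2 + 1.341)(120) = 360.7, or +6.0%.

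The same 230 h visit on three assumed profiles:

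| Day 3 score → Day 7 score | Placed at 168 h | Interpolated | Difference |
|---|---|---|---|
| 2 → 1 (A) | 340.25 | 360.7 | +6.0% |
| 3 → 0 | 352.25 | 413.6 | +17.4% |
| 2 → 3 | 460.25 | 439.8 | −4.4% |

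Under either inclusion limit the visit is dropped, which leads to a third value through re-scoring or imputation.

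**4. Time zero, if taken literally.** On profile A, with the end held at 168 h, an origin 3 h before the first dose gives 353.75 and one 3 h after gives 326.75, against 340.25. That is 13.5/340.25, about 4% either way. With an origin 6 h after the dose, the 3.5 h assessment falls at −2.5 h and the first interval is negative.

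**5. Visits inside the window.** With time zero at first dose and the Day 7 score placed at 168 h, profile A gives 340.25 for any visit from 144 to 192 h. This needs the placement to come first. If the 7-day condition were applied to actual times, a visit at 180 h would be dropped. The SAP does not state the order.

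**The case against.** The best defence is that these are drafting slips with an evident meaning. The same section says that the baseline score is the one at time zero, the endpoint runs from baseline, and the SAP elsewhere counts from first dose. Nothing calls antivenom the infusion, and an antivenom origin can produce negative intervals, so nobody would program it. The 8-day limit matches the upper edge of the visit window and can be read as choosing which visit qualifies. The exceptions state hours, which could be taken to govern. Visits past 216 h are outside the protocol window, and no frequency is given for them.

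Most of this stands, and it limits the size of the problem. It does not make the text consistent: even if the hours govern, both limits still exclude visits at 240 h or later.

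A reader might infer three stronger points that the documents do not support.

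- **That 7 days conflicts with 168 h.** They are the same limit. The 144 h figure alone is also the lower edge of the 7 ± 1 day window.
- **That placing Day 3 at 48 h for the NPRS AUC contradicts placing Day 7 at 168 h.** Under the protocol schedule, Day 2 falls 12 to 18 h after the 8-10 h assessment, at 20 to 28 h. Day 3 follows by at most about 24 h, at up to 44 to 52 h. Day 7 is 7 days after dosing. Both placements match nominal visit times.
- **That moving an in-window score to 168 h is itself an error.** The shift is at most 24 h, the rule gives one answer, and interpolating instead is a choice between methods.

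**Conclusion.** The point holds in a limited form. Three rules fail as written: the time origin, the inclusion limits against the late-visit exception, and the Day 7 and Day 10 hours. The AUC is not unique under the literal origin, for Day 7 visits at 216 to 240 h, or for visits whose inclusion depends on which limit is applied and when. For visits at 144 to 192 h it is unique, given time zero at first dose and placement at 168 h before any limit.

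For an affected visit at 230 h, the two readings differ by between −4.4% and +17.4% on the assumed profiles. These illustrate a single patient's value. The effect on the treatment comparison cannot be computed without score trajectories and late-visit counts. Nothing here shows bias between arms, and the sample size is unaffected. The endpoint's place in the testing sequence makes correction before unblinding worthwhile.

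**What to change.** Rewrite SAP 6.1.7.2 as follows.

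1. Define time zero as the time of the first oral dose of study drug and delete the infusion wording.
2. State one inclusion limit that is compatible with the late-visit exception, and say that the 168 h placement or interpolation is done before the limit is applied.
3. Use one cut-off for late visits, in hours. The preferred choice is the end of the protocol window: for any Day 7 visit after 192 h, interpolate between Day 3 and the actual Day 7 time to obtain the 168 h score. No out-of-window score is then moved unadjusted; at present the shift can approach 240 − 168 = 72 h.

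Interpolating every early visit toward Day 14, or carrying the last score forward, is optional. If adopted, either would have to be reconciled with the multiple imputation in SAP 6.1.4.

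The cost is one SAP paragraph and a matching edit to the derivation program, with no change to data collection or sample size.
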